## **2.3 Data and Analysis Quality Control**

The trial monitoring plan for Clinical Trials Sponsored by Thirty Respiratory Limited for this study will detail the quality assurance and quality control systems to be implemented to assure the quality of the data. Similarly, the quality control of the statistical analysis will follow the SOPs of institution performing the statistical analysis.

# **3. EFFICACY AND SAFETY VARIABLES**

## **3.1 Efficacy**

The primary objective in part 1 (Dose Finding Phase) is to determine the maximum tolerable dose (MTD) and the recommended therapeutic dose (RTD) of the single agent RESP301. For these decisions individual and cohort stopping criteria were defined, see section 7.7.2 and 7.7.3 of the protocol. In a Safety Advisory Committee (SAC) meeting prior to part 2 of this study these doses will be determined. Hence no single primary and/or secondary endpoint for part 1 was defined.

In part 2 (Expansion Phase), the primary endpoints are:

- Percentage of patients entering the dormant period who, having experienced and correctly reported an exacerbation, commence self-administration of the treatment at home on the day the treatment is delivered.
- Percentage of patients who, having experienced and correctly reported an exacerbation, receive the treatment within 48 hours of reporting their exacerbation.
- Compliance with RESP301 administration schedule over the treatment period: for those participants commencing treatment, the percentage of total doses taken.

The secondary endpoints, which will be analyzed by treatment dose and separately in the sub-group of patients who had a positive test result for SARS-CoV-2 are defined as:

- % of participants able to tolerate the test dose in Part 1(a), Part 1(b) and Part 2, i.e. able to complete the test dose without any of the following:
  - o Troublesome cough, chest pain or tightness, bronchospasm or dyspnea that is deemed unacceptable by the patient.
  - o methemoglobin >5% during or >3% post dose (30 or 60 mins)
  - o any treatment-related AE that led to participant not being able to complete the test dose, and/or be suitable to be enrolled into the dormant period in the Investigator's opinion
  - o for the first 50 patients who will undergo pre and post-test dose spirometry, >20% reduction in FEV1 from pre-test dose to post

---

test at 60 min dose with symptoms listed above (patients with >20% reduction in FEV1 without symptoms would be offered the option to continue in the study).

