	
the patient is willing to continue in the study, they will have a rapid delivery of a study pack containing study IMP and nebuliser and other equipment for the trial.
 
Note that if COVID-19 is suspected, the patient will be advised to follow the prevailing NHS guidance on testing for COVID-19 taking into account any specific recommendations for patients with COPD or bronchiectasis. Where serial SARS-CoV-2 swabs are undertaken, data will be collected for analysis.
 
During the treatment period, lasting 7 days, at home/ community setting, patients will be asked to:
 

• Administer RESP301 three times daily at the RTD

• Take daily temperature measurements

• Complete a daily diary to record treatment doses

• Attend a daily call with study coordinator to check compliance, assist with issues with product, and report any AEs and changes to medications or medical history, including COVID-19 test results, if available

 
Each participant will receive a maximum of one course of treatment of RESP301 during the study. Remote follow up visit will be carried out approximately 14 and 28 days following end of treatment to record any AEs and changes to medications or medical history, including COVID-19 test results, if available. Additionally, participants whose symptoms had not returned to baseline by the end of treatment period, will be followed up with a phone call 2 weeks post end of treatment.

Endpoints	
Primary endpoint:
 

• Proportion of patients tolerating RESP301 at each dose level in Part 1 (according to pre-defined criteria)

• Feasibility of self-administering RESP301 treatment with nebuliser in terms of:

○ percentage of patients who, having experienced and correctly reported an exacerbation, commence self-administration of the treatment on the day the treatment is delivered

○ compliance with RESP301 administration schedule over the treatment period: for those participants commencing treatment, the percentage of total doses taken

 
Secondary endpoints:

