	
inhaled bronchodilator 10 minutes before receiving a single dose of RESP301 at the MTD. Participants from Part 1b may also enter Part 2 of the study if they fullfill eligibility criteria.
 
Part 2:
 
We aim to recruit 150 patients from secondary care and primary care sites in the UK (includes eligible participants from Part 1 of the study). A minimum of 50 consented participants will receive an initial test dose of RESP301. We estimate that over 12 months, a minimum of 30 of the enrolled participants will exacerbate. These participants will commence self-administered RESP301 treatment. Non-exacerbating participants will receive no further study interventions.

Inclusion criteria	

1. Female of non-childbearing potential or male <math>\geq 35</math> years of age, at the time of signing the informed consent

2. Able and willing to provide informed consent

3. Spirometry-confirmed diagnosis of COPD (FEV1/FVC<math><0.7</math> post-bronchodilator at screen 1, or from historical data) or computerised tomography (CT) proven bronchiectasis

4. Part 1 only: FEV1 <math>\geq 50\%</math> predicted at screen 1 (i.e. FEV1 prior to any in-clinic administered short acting bronchodilator)

Exclusion criteria	

1. Unable to safely use a nebuliser as required by the study according to Investigator's opinion

2. Severe COPD or bronchiectasis defined as FEV1 % predicted <math><20\%</math> or requiring non-invasive ventilation

3. History of methaemoglobinemia

4. Baseline methaemoglobin concentration (using fingertip sensor) <math>> 2\%</math>

5. Uncontrolled or severe asthma or history of severe bronchospasm

6. Presence of tracheostomy/inability to provide spirometry or contraindication for performing spirometry

7. Allergy to any of the components of the study intervention

8. Participation in other clinical investigations utilising investigational treatment within the last 30 days / 5 half-lives whichever is longer

9. Deemed unlikely to be able to adhere to protocol in view of investigator

10. Any subject who in the opinion of the investigator would not be best served by participating in this clinical trial

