## **8.2 Dormant period**

During the dormant period, the participants will receive monthly follow-up calls to remind them to contact the study team if they start experiencing exacerbation symptoms.

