## **4. SAMPLE SIZE JUSTIFICATION**

The primary objective of this study is to determine the MTD and RTD of RESP301 and to assess feasibility. No formal sample size calculation was performed. In Part 1, we aim to recruit up to 56 participants (8 per dose group) to receive one dose of RESP301 (alone or in combination).

In Part 2, we aim to recruit around 150 patients from secondary care and primary care sites in the UK into the dormant period. The first 50 consented participants will receive an initial test dose of RESP301 before progressing to the dormant period. If, based on the first 50 participants, the DMC determines that it is safe to do so, the remaining consenting participants will not be required to receive a test dose before progressing to the dormant period. It is estimated that over 12 months, 30 of the 150 enrolled participants will exacerbate. These participants will commence self-administered RESP301 treatment. Non-exacerbating participants will receive no further study interventions.

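### The first Part 2 feasibility percentage has no stated denominator, and both feasibility percentages leave out exacerbations that were not correctly reported

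*SAP*

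**What the plan says.** The protocol synopsis (Section 1, Endpoints) gives the first Part 2 feasibility measure as the "percentage of patients who, having experienced and correctly reported an exacerbation, commence self-administration of the treatment on the day the treatment is delivered". SAP Section 3.1 words it as "Percentage of patients entering the dormant period who, having experienced and correctly reported an exacerbation, commence self-administration" at home on the delivery day, so it adds a reference to dormant-period entry. The 48-hour item that follows in the same SAP list has no such reference: "Percentage of patients who, having experienced and correctly reported an exacerbation, receive the treatment within 48 hours of reporting their exacerbation". The synopsis lists that item as secondary and the SAP lists it as primary.

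The readable text does not state a numerator and denominator, and it does not define correct reporting. The synopsis gives a minimum symptom duration of 24 hours and a 72-hour contact window but does not tie either to the term.

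On the analysis set:
- SAP Section 5.10 summarises these endpoints on the Full Analysis Set (FAS) and the Per-Protocol Set.
- SAP Section 5.2 limits the FAS to patients who inhaled study medication and have a post-treatment assessment.
- SAP Section 5.1 treats patients who received no study medication as screening failures and shows them only in the disposition table.
- Protocol Table 10-1 instead defines an ITT population of everyone enrolled into the treatment period.

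In the dormant period, Protocol Section 8.2 provides for "monthly follow-up calls to remind them to contact the study team if they start experiencing exacerbation symptoms". The synopsis says nothing else is collected in that phase unless symptoms occur. SAP Table 3 marks neither symptom review nor AE/SAE review in the dormant column.

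On numbers, SAP Section 4 says "In Part 2, we aim to recruit around 150 patients from secondary care and primary care sites in the UK into the dormant period" and "It is estimated that over 12 months, 30 of the 150 enrolled participants will exacerbate". The protocol synopsis says "We estimate that over 12 months, a minimum of 30 of the enrolled participants will exacerbate".

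**The concern.** A primary objective is to learn whether symptomatic patients can be treated in the community. The first step that can fail is the patient recognising the exacerbation and calling in time. Both percentages start after that step. Late, incorrect or absent reports leave the denominator, no readable endpoint shows how many there were, and the readable plan has no stated way to record the unreported ones.

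The SAP wording adds a second uncertainty, because it is not clear whether the first percentage is out of correct reporters or out of everyone who entered the dormant period. The FAS adds a third, because it can remove exactly the patients who reported correctly and then failed to start. The analysis is purely descriptive, so the percentage is itself the primary result, and its meaning depends on its denominator.

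**Working it through.** **Inputs from the documents**
- Dormant entrants: about 150 (SAP Section 4).
- Expected exacerbators: 30 (SAP Section 4), or at least 30 (protocol synopsis).
- Exacerbation rate in moderate COPD: 0.85 per person (Protocol Section 3.1), taken here as per year, which is an assumption.
- Test dose: first 50 Part 2 participants, possibly none after that (SAP Section 4).

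**Assumptions, not in the documents**
- Share of exacerbations correctly reported, q: 50% to 100%.
- Share of correct reporters who start on the delivery day: 80% for illustration.

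**1. The plan's own figure.** 30/150 = 20.0%. The readable text gives no derivation, no target percentage and no formal sample size.

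**2. Strict reading of the SAP wording.** If all 30 report correctly and 24 start on time (exact Clopper-Pearson 95% intervals):
- out of correct reporters: 24/30 = 80.0% (61.4% to 92.3%);
- out of dormant entrants: 24/150 = 16.0% (10.5% to 22.9%).

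If all 30 start on time, the dormant-entrant figure reaches its ceiling of 30/150 = 20.0% (13.9% to 27.3%). The ratio of the two denominators is 150/30 = 5.

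Two things shrink that ratio.
- *More exacerbations.* At 0.85 per year under a Poisson model, 1 − exp(−0.85) = 0.573, so 150 × 0.573 = 86 participants exacerbate and the ratio is 150/86 = 1.7.
- *The FAS.* Suppose test doses stop at 50, a third of the 30 exacerbators (10) had one, all 30 start, all dosed patients have a post-treatment assessment, and carry-over from Part 1 is ignored. The FAS is then 50 + 20 = 70 and the ceiling is 30/70 = 43%. The 20% ceiling needs essentially all 150 to have been dosed.

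**3. Intended reading: conditioning on correct reporting.** Let E be all exacerbators, R = qE the correct reporters and S those who start on time. Then S/R = (S/E)/q, so the planned percentage exceeds success among all exacerbators by 1/q. With S/R = 80%:

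| q | S/R | S/E | Factor 1/q |
|---|---|---|---|
| 100% | 80% | 80% | 1.0 |
| 90% | 80% | 72% | 1.11 |
| 80% | 80% | 64% | 1.25 |
| 60% | 80% | 48% | 1.67 |
| 50% | 80% | 40% | 2.0 |

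The same factor applies to the 48-hour delivery percentage.

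**4. Effect of the FAS on the intended reading.** Take 30 correct reporters, 24 starters and 6 non-starters, of whom k never inhaled drug. Assume everyone who inhaled drug meets the other FAS condition. The FAS result is 24/(30 − k):
- k = 0: 24/30 = 80.0%
- k = 2: 24/28 = 85.7%
- k = 4: 24/26 = 92.3%
- k = 6: 24/24 = 100%

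If test doses stop at 50 of 150 and Part 1 carry-over is ignored, two thirds of entrants are undosed. That points to k = 6 × 2/3 = 4.

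**The case against.** The strongest reply is that the protocol's conditional percentage is legitimate. The endpoint is labelled as feasibility of self-administration with the nebuliser, and for that question the patients who reported and could be sent a pack are a proper denominator. This stands: the percentage is not an arithmetic error and is not biased for the quantity it names. It falls short only against the broader objective of treating symptomatic patients in the community.

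On the wording, a reader might infer that the SAP uses 150 for the first percentage and about 30 for the second, so that the first will come out several times too small. The documents do not support this. The two items share the same grammar, and the contrast arises only if one is parsed strictly and the other naturally. Every treated patient comes from the dormant period, so the added words may merely name the source population. A denominator of 150 also ignores the FAS.

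Protocol Sections 10.4.2 and 8.3 and Table 4-1 are partly redacted and may define the denominator or correct reporting, so absence there cannot be asserted. SAP Section 3.1 is readable and gives neither.

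The SAP will also print sample sizes with its frequencies (Section 5.1), and the protocol plans a participant flow diagram (Section 10.4.1). These would show which denominator was used. They would not count exacerbations that were never recorded, nor restore undosed reporters to the endpoint table.

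**Conclusion.** The point holds as a gap in specification that is worth closing, in three parts.
- The SAP wording departs from the protocol and leaves the denominator open. A strict reading caps the result near 20% if 30 of about 150 exacerbate and nearly all are dosed; correct reporters were probably meant.
- On that reading, both percentages describe delivery and self-administration after successful reporting, and exceed success among all exacerbators by 1/q. Since q is not given, the size is unknown: none at q = 100%, a factor of 2.0 at q = 50%.
- The FAS can drop correct reporters who never inhaled drug. In the example this moves 80% to between 85.7% and 100% when 2 to 6 of the 6 non-starters had no earlier dose.

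The low figure from the strict reading and the 1/q excess belong to different readings and cannot both apply. It would go too far to say that the plan's figure will be inflated or will be several times too small.

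**What to change.** 1. In SAP Section 3.1, delete *entering the dormant period* from the first item.
2. State that the denominator of both percentages is all dormant-period participants who correctly reported an exacerbation, whether or not they inhaled drug, and that the FAS does not apply to these two. Define correct reporting in the SAP, consistently with any definition in the unredacted protocol.
3. Add a supplementary row with the same numerators out of all exacerbations known to the study team, including late and out-of-window callers. Give n/N at each step: known, reported, correctly reported, received within 48 hours, started on day of delivery.
4. Optionally, record at the existing monthly call whether an unreported flare has occurred.

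Items 1 to 3 cost SAP wording and one more table row, and the added percentage may be less favourable. Item 4 changes data collection and would need an eCRF and protocol amendment, and recall will be imperfect. The SAP cites a 2024 drug dictionary against a November 2021 protocol, so data collection may already be well advanced (an inference). Items 1 to 3 do not depend on item 4.

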	
Part 2: Expansion Phase
 
A test dose of RESP301 at RTD will be administered during the baseline visit under clinical supervision in a minimum of 50 patients. Patients who tolerate the test dose will progress to the Dormant Period to which a further 100 participants will also be recruited with or without a test dose (depending on review of safety data after the first 50 patients). Participants in the Dormant Period will inform the clinical team if symptoms develop indicative of a possible respiratory infection (exacerbation) and will then progress to the Treatment Period, in which eligible participants receive RESP301 by courier or at a subsequent clinic visit for treatment by self-administration at home. During the Treatment Period, RESP301 is taken at the RTD three times a day at least 4 hours apart for 7 days alongside normal Standard of Care (SOC) (treatment period may extend into Day 8 depending on time of commencing on Day 1). During the Treatment Period participants may use rescue medication as required.

Comparator	Not applicable
Study design	
This is a single arm, non-randomised, open-label study.
 
Part 1(a): Dose Finding Phase
 
Up to 48 eligible participants will be administered single ascending doses of RESP301 under clinical supervision to determine the MTD, according to the following schedule:
 

• 8 participants to receive RESP301 at a dose of 1 ml

• 8 participants to receive RESP301 at a dose of 2 ml

• 8 participants to receive RESP301 at a dose of 3 ml

• 8 participants to receive RESP301 at a dose of 4 ml

• 8 participants to receive RESP301 at a dose of 5 ml

• 8 participants to receive RESP301 at a dose of 6 ml

 
Safety data will be reviewed by the PIs and Sponsor after each dose before proceeding to the next higher dose.
 
Safety data will include:
 

• Treatment-related Adverses Events including troublesome cough, chest pain or tightness, bronchospasm or dyspnoea the patients finds intolerable

• Changes in FEV1

• Changes in methaemoglobin level

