	
Part 2: Expansion Phase
 
Once the Recommended Therapeutic Dose has been determined in Part 1 (a), a minimum of 150 patients will be enrolled in to the Expansion Phase, which is split into 3 periods. For participants taking part in the Dose Finding Phase (Part 1), eligibility criteria will be reassessed prior to entering Part 2 of the trial.
 
1) Baseline visit
 
In a minimum of 50 participants the following will be performed:
 

• Administration of a test dose of RESP301, at the RTD

• Assesses response to RESP301 (incl. recording any AEs, FEV1 pre- and post dose and monitoring methaemoglobin levels pre-, during and post- administration, using fingertip sensor; methaemoglobin level should be <=2% before, <=5% during, and <=3% at 30-60 mins post dose (i.e. if still >3% at 30 mins, check again at 60mins post dose).

 
During the visit participants who satisfactorily tolerate the test dose will then be enrolled into the “dormant period” of the study for 12 months.
 
An independent Data Monitoring Committee will review the data from the 50 participants that received the RTD. Based on the data from these participants, it will be decided whether test doses should be administered to further participants before enrolling them into the Dormant Period.
 
2) Dormant Period
 
Dormant period patients are requested at the baseline visit, and monthly follow-up calls, to inform the study team if they develop exacerbation symptoms indicative of a respiratory infection. There will be no other study procedures or data collection during the “dormant study phase” unless the participant experiences exacerbation symptoms.
 
3) Treatment Period
 
A patient who experiences exacerbation symptoms for at least 24 hours should contact the study team as soon as practicable to allow a study interaction to be undertaken remotely (via video link, if possible), within 72 hours of onset of at least one of the following: fever (<math>>38.0^{\circ}\text{C}</math>), systemic malaise, increased cough or wheeze, increased sputum volume or increased purulence. During the remote visit the patient’s symptoms will be discussed and if

--	--

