## **5. METHODS OF ANALYSIS AND PRESENTATION**

### **5.1 General Principles**

The statistical analysis will be performed using the validated software package SAS version 9.4 or higher (SAS Institute Inc., Cary, NC 27513, USA).

All recorded and derived variables will be presented by treatment group and visits (if appropriate) using descriptive summary tables (continuous data: sample size, mean, standard deviation (SD), minimum, median, maximum; categorical data: sample size, absolute and relative frequency).

The mean and median will be presented to one more decimal place than the raw data. The SD will be presented to two more decimal places than the raw data. The percentages will be presented to 1 decimal place. In all the summaries, the treatment groups will be displayed in the following order: part 1 (RESP301 1 ml, 2 ml, ...6 ml, RESP+Vent 6 ml) and then part 2.

For all parameters, baseline is defined as the last available pre-treatment value (i.e. the last non-missing value available before study drug administration. In general, missing data will be treated as missing and no attempts will be made to impute values for missing data.

No formal interim efficacy analyses are planned in this study; however, several safety interim analyses by the Safety Advisory Committee (SAC) will be performed as detailed in the protocol, see section 7.7 for part 1 and an Independent Data Monitoring Committee (IDMC) will review the safety data on an ongoing basis as described in the DMC charter, see section 10.6 of the protocol.

Subjects who did not receive any study medication (screening failures) will be listed separately and not presented in any table or figure, except in the patient's disposition table.

The versions of the following international dictionaries (MedDRA version 26.1 and WHO DD, version 2024) will be used for medical coding:

Adverse events: Medical Dictionary for Regulatory Activities (MedDRA).

Medical Histories: Medical Dictionary for Regulatory Activities (MedDRA).

Medications: World Health Organization (WHO) Drug Dictionary including Anatomical Therapeutic and Chemical (ATC) classification.

If a medication in the drug dictionary (DD) table is associated with more than one ATC code, the first ATC code will be assigned to that medication.

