## 15.2 Efficacy Results

Table 1.1	Summary of primary endpoints, part 2 – FAS/PPS set
Table 1.2	Summary of secondary endpoints – FAS/PPS set
Table 1.3	Summary statistics of spirometry over time – FAS/PPS set
Table 1.4	Summary of VAS scales – FAS/PPS set
Table 1.5	Summary statistics of explorative/sub-group analyses, if any – FAS/PPS set

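### The same-day start endpoint allows less time the later the pack arrives, and no elapsed time to first dose is specified to help interpret it

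*SAP*

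**What the plan says.** SAP 3.1 lists three Part 2 primary endpoints, and two concern timing. One counts participants with a correctly reported exacerbation who "commence self-administration of the treatment at home on the day the treatment is delivered". The other counts those who "receive the treatment within 48 hours of reporting their exacerbation". The protocol synopsis has the first as a primary endpoint in nearly the same terms ("commence self-administration of the treatment on the day the treatment is delivered") and places the 48-hour endpoint among the secondary ones.

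On supply, the synopsis says eligible participants "receive RESP301 by courier or at a subsequent clinic visit for treatment by self-administration at home". It accepts that the starting hour varies, since the "treatment period may extend into Day 8 depending on time of commencing on Day 1". The remote contact that precedes supply is to take place "within 72 hours of onset of at least one of the following" listed symptoms (synopsis, Part 2, Treatment Period).

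On reporting, SAP 15.2 lists Table 1.1, "Summary of primary endpoints, part 2 – FAS/PPS set", and no table of elapsed times to first dose. SAP 5.10 makes all analyses of these endpoints descriptive. SAP 4 expects 30 of 150 participants to exacerbate and go on to treatment.

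**The concern.** A yes/no endpoint cut at the end of a calendar day has no fixed length: the time a participant has to succeed is whatever remains of the day when the pack arrives. Two participants who behave identically can be scored differently because one was supplied in the morning and the other in the evening.

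The 48-hour endpoint does not fill the gap. It stops at receipt and is itself a yes/no cut. Neither endpoint tells the reader how long after delivery, report or symptom onset the first dose was inhaled, although the stated rationale is to treat these patients in the community when viral symptoms begin.

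At stake is how a feasibility result is read. A low same-day percentage might mean that participants struggled to start, or only that packs came late in the day. A high one could coexist with late treatment relative to onset. Without elapsed times these cannot be told apart.

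**Working it through.** **The plan's own figure.** The only number bearing on this endpoint is its expected size: 30/150 = 20%. It is given without derivation, so there is nothing further to reproduce. No alpha, power or target is stated.

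**Step 1: time allowed.** Hours left before midnight = 24 − delivery hour. This follows from the definition alone.

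| Delivery | 09:00 | 12:00 | 15:00 | 18:00 | 20:00 | 21:00 |
|---|---|---|---|---|---|---|
| Hours left | 15 | 12 | 9 | 6 | 4 | 3 |

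**Step 2: the order can reverse.** Delivered 08:00 and started 22:00 is 14 h and a success. Delivered 20:00 and started 08:00 the next day is 12 h and a failure.

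**Step 3: both timing endpoints together, as limiting cases.** A participant who reports at 72 h from onset, is supplied 48 h later in the morning and starts 14 h after that passes both: 72 + 48 + 14 = 134 h from onset. One who reports at 24 h, is supplied 2 h later in the evening and starts 12 h later fails the same-day endpoint at 24 + 2 + 12 = 38 h. The first case needs reporting to fall exactly at 72 h, because the 48-hour clock starts at reporting. These cases show what the definitions permit, not what is likely.

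**Step 4: illustrative size.** Assumptions, none of them from the documents: the lag from delivery to first dose is lognormal with median m and log-SD s, and does not depend on delivery hour h. Then

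P(same-day start) = Φ([ln(24 − h) − ln m] / s).

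Example: h = 15, m = 4, s = 0.8 gives Φ(ln(9/4)/0.8) = Φ(1.01) = 0.84. With s = 0.8:

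| Median lag | 09:00 | 15:00 | 18:00 | 20:00 | Drop, 09:00 to 20:00 |
|---|---|---|---|---|---|
| 1 h | 1.00 | 1.00 | 0.99 | 0.96 | 0.04 |
| 2 h | 0.99 | 0.97 | 0.92 | 0.81 | 0.18 |
| 4 h | 0.95 | 0.84 | 0.69 | 0.50 | 0.45 |
| 8 h | 0.78 | 0.56 | 0.36 | 0.19 | 0.59 |

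Varying s: at m = 1 h the drop is 0.00 (s = 0.5) or 0.11 (s = 1.2); at m = 4 h it is 0.50 or 0.36.

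If one further assumes that nobody starts after 22:00, 24 is replaced by 22. At s = 0.8 the values for 09:00/15:00/18:00/20:00 become 1.00/0.99/0.96/0.81 for m = 1 h and 0.93/0.76/0.50/0.19 for m = 4 h.

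**Step 5: a fixed window.** P(start within 24 h) = Φ([ln 24 − ln m]/s). At s = 0.8 this is 1.00, 1.00, 0.99 and 0.92 for m = 1, 2, 4 and 8 h. Delivery hour no longer enters the formula.

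**Step 6: precision at n = 30.** An observed 24/30 (80%) has an exact 95% confidence interval of 61% to 92%.

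**The case against.** The strongest reply is that the size rests wholly on assumptions. Symptomatic participants waiting for a rapidly delivered pack may well start within an hour or so. At a 1-hour median lag and s = 0.8 the midnight cut moves the result by only 4 points between 09:00 and 20:00. This stands. A reader might infer that the endpoint reflects delivery hour as much as the participant; the documents give no delivery-hour or lag distribution from which to show that. Nor is the courier the only route, since supply may be at a clinic visit.

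Second, SAP 5.1 promises that "All recorded and derived variables will be presented by treatment group and visits (if appropriate) using descriptive summary tables". A reader might infer that elapsed delays will never be summarised. That goes too far: a delay would be covered if it were recorded or derived. But no delay is named as a variable, so the sentence does not secure the output. Supply delay has its own endpoint, though only as a yes/no at 48 hours.

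Third, it is tempting to argue that dichotomising costs power. The plan has no hypothesis, threshold or test, and non-starters have no delay to analyse, so a power comparison does not apply.

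Fourth, protocol 7.4, 8.3, 8.4 and 10.4.2 are partly blacked out, and the eCRF is not available. A time definition or recorded clock times may exist there, and any missing rationale for the cuts cannot be held against the plan. SAP 3.1, however, is readable and defines the endpoint without one.

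Finally, the percentage has a merit that elapsed times lack: participants who never start count against it. A median among starters alone would hide that failure, so elapsed times should support the endpoint and not replace it.

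**Conclusion.** The concern holds in a limited form. By its definition, the same-day endpoint allows a time that shrinks with delivery hour, so the percentage can depend materially on when the pack arrives as well as on the participant. The effect runs from near nil (short lags, or early delivery with moderate lags) to about 45 points (09:00 against 20:00 at a 4-hour median lag, s = 0.8), and more at longer lags. These sizes rest on an assumed lognormal lag and assumed delivery hours; the shrinking window and the possible reversal of order do not.

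No elapsed time from delivery, report or onset to first dose is specified as a variable or listed as an output in the readable text. Because there is no success threshold and everything is descriptive, no formal decision changes. Severity is minor.

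**What to change.** Keep the same-day percentage as the protocol-defined primary endpoint. In SAP 3.1, and in Table 1.1 of SAP 15.2, add these supporting rows:

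- **Fixed window.** The percentage starting within a fixed elapsed window of delivery, for example 24 hours, among all who correctly reported an exacerbation, with non-starters counted as not started. The window is for reporting only and is not a rule on when to treat. A 24-hour window contains the same clock hours whenever it begins. It may sit near 100% if lags are short, so it should not stand alone.
- **Elapsed hours.** Median, quartiles and range of hours from report to receipt, from delivery to first inhalation, and from symptom onset to first inhalation, among those with the event, with the number of non-starters shown beside them.

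State the denominator in the table. Table 1.1 is planned on the FAS and PPS, and the FAS requires inhaled medication, so a non-starter who had no test dose could otherwise drop out. Add a sentence that the same-day percentage is to be read alongside these rows.

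The cost is SAP wording and a few rows in one table. The 48-hour endpoint already needs report and receipt times. The small added burden is capturing clock times for delivery and first dose, plus a time of symptom onset, using the diary with the daily call as back-up.
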